12.4 Interim Analyses

12.4.1 Interim Efficacy/Futility Analysis

A single interim analysis will be performed on the primary efficacy endpoint (difference in the probability of TTH within 6 minutes) using data on the TTH Population, defined as all subjects who were randomized, received study intervention, and had a TTH assessment recorded regardless of whether the measurement was censored.

The study will be monitored by an Independent Data Monitoring Committee (IDMC). The IDMC will be provided with blinded efficacy data at the time of the interim analysis. Detail of the activities associated with the IDMC will be provided in an IDMC Charter. In the following, we provide the description of the *a priori* defined interim analysis plan that will be used in the trial.

In making a decision to recommend early termination of the study, the IDMC shall be guided by a formal stopping rule based on the primary efficacy endpoint. The test statistic shall be the estimated difference in the probability of TTH within 6 minutes between the HEMOBLAST™ and G+T arms as described in Section 12.3.1.2. The clinical trial may only be stopped early either for reasons of futility (the observed difference in the probability of TTH within 6 minutes comparing HEMOBLAST™ to G+T is not sufficiently high enough to warrant continuation of the trial) or efficacy (the observed difference in the

probability of TTH within 6 minutes comparing HEMOBLAST™ to G+T is sufficiently high enough to conclude non-inferiority).

The formal stopping boundaries will be determined by futility and efficacy boundaries defined within the unified family of group sequential stopping rules.²⁰ In the notation of the latter paper, the stopping rule will be based on a one-sided group sequential design testing an upper alternative hypothesis at a level of significance $\alpha = 0.025$ with a lower (futility) stopping boundary relationship specified by $P_a = 0.8$ and an upper (efficacy) stopping boundary relationship specified by $P_d = 0.8$ (a boundary with conservatism in between the Pocock type boundary and an O'Brien-Fleming type boundary).^{21, 22}

The trial will utilize a 2:1 randomization scheme (HEMOBLAST™ : G+T). Randomization will be stratified by surgery indication and it is anticipated that accrual to each surgical indication will be roughly equal. It is envisioned that one interim analysis will be performed during the monitoring of the study, occurring after outcomes have been observed for 240 randomized and treated subjects belonging to the TTH Population (approximately 160 subjects treated with HEMOBLAST™ under 2:1 randomization), and may continue to a maximal sample size of 400 subjects (approximately 267 subjects treated with HEMOBLAST™ under 2:1 randomization). Although the above interim analysis is pre-defined, final inference for comparable efficacy will treat the futility boundary as non-binding (implying that the type I error rate for the trial will be bounded at or below .025 even if the futility boundary is crossed at the interim analysis but the trial continues on).

Under such a monitoring schedule and assuming a probability of TTH within 6 minutes of 88% in both the HEMOBLAST™ arm and the G+T arm, a maximal sample size of 400 treated subjects (267 in the HEMOBLAST™ arm and 133 in the G+T arm) will provide approximately 80.1% power to determine comparable efficacy based upon a 10% non-inferiority margin of absolute difference in the probability of TTH within 6 minutes. Of particular note, if the study were to stop in favor of comparable efficacy at the interim analysis after 60% of the maximal sample size were accrued, data would be available on approximately 160 patients in the TTH Population treated with HEMOBLAST™ plus up to an additional 50 lead-in subjects. Assuming equal accrual to each surgical indication this would provide safety data on roughly 70 subjects treated with HEMOBLAST™ for each surgery type.

Enrollment will continue in parallel with the interim analysis. Thus, if the interim analysis supports early termination of the clinical investigation, the number of subjects included may be higher than the number available at the time of the interim analysis. All available data for the analysis populations defined above will be included in the final analysis and report.

Under the planned schedule of one interim analysis at 240 treated subjects and a assumed 6 min TTH success rate of 88% in the G+T arm, Table 9 presents the stopping boundaries at the interim and final analysis for the specified stopping rule expressed as the normalized fixed sample z-statistic for testing non-inferiority and the corresponding fixed sample p-value.

Table 9: Stopping boundaries for a level 0.025 one-sided design with a single interim analysis (NON-BINDING FUTILITY ($P_a = 0.8$) AND EFFICACY ($P_d = 0.8$) occurring at 240 patients, and a maximal sample size of 400 patients (2:1 randomization). The boundaries assume a 88% probability of TTH within 6 minutes on the G+T arm and a 10% non-inferiority margin. Stopping boundaries are expressed as the difference in the probability of TTH within 6 minutes (HEMOBLAST™ – G+T).

Analysis	Total Sample Size (H, G+T)*	Futility (lower) Stopping Boundary		Comparable Efficacy (upper) Stopping Boundary	
		Z-statistic	P-value	Z-statistic	P-value
1	240 (160, 80)	0.788	0.215	2.373	0.009

2	400 (267, 133)	2.036	0.021	2.036	0.021
---	----------------	-------	-------	-------	-------

* H : HEMOBLAST™

Thus, according to the above table, if the observed Z-statistic for testing non-inferiority (Cochran-Mantel-Haenszel estimate minus the non-inferiority margin, divided by the estimated standard error) is 0.788 *or lower* when 240 subjects have been treated and observed for TTH on the study, the stopping rule would suggest that the study be terminated early with a decision that it was futile to continue the trial because there was not sufficient evidence that HEMOBLAST™ would be determined to be comparably efficacious if the study were to continue. Alternatively, if the observed Z-statistic for testing non-inferiority is 2.373 *or higher* when 240 subjects have been treated and observed for TTH on the study, the stopping rule would suggest that the study be terminated early with a decision in favor of comparable efficacy between the two products. A repeated 95% confidence interval for the stratum-weighted difference in proportions, corrected for the stopping rule, will be computed at the completion of the trial. In the event that true probability of TTH within 6 minutes for G+T arm is observed to be different from 88% or the timing of the interim analysis differs, the stopping boundaries will be adjusted to maintain a one-sided type one error rate of 0.025 as described in Section 12.4.3.

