8 INDEPENDENT DATA MONITORING COMMITTEE

An Independent Data Monitoring Committee (IDMC) will be formed to review data from the clinical investigation to evaluate the safety and efficacy of the investigational device. The IDMC will be formed prior to subject enrollment and the names, affiliations, and academic backgrounds of all members will be provided to the Regulatory/Competent Authority.

The members of the IDMC are responsible for safeguarding the interests of study participants, assessing the safety and efficacy of study procedures, and reviewing the overall conduct of the clinical investigation. The IDMC will review clinical investigation data to evaluate study conduct, investigational device safety, and scientific validity and integrity of the investigation.

The IDMC will provide recommendations regarding the implementation and progress of clinical investigation, including continuation, suspension and/or termination of the clinical investigation. A separate charter for the IDMC will define and describe:

- Roles and responsibilities;
- Membership;

- Frequency of meetings; and
- Documentation and reporting.

A separate CEC (Clinical Events Committee) will be formed to review all SAEs and corresponding data for each SAE. The CEC will be formed prior to subject enrollment and the names, affiliations, and academic backgrounds of all members will be provided to the Regulatory Authority.

The members of the CEC will be responsible for reviewing and adjudicating SAEs for relatedness to the hemostatic device and expectedness. A separate charter for the CEC will define and describe:

- Roles and responsibilities;
- Membership;
- Frequency of meetings;
- Adjudication process; and
- Documentation and reporting.

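### Does giving the IDMC blinded efficacy data stop it from applying a between-arm stopping rule?

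*Protocol*

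**What the plan says.** Protocol 12.4.1 plans one interim analysis of the primary endpoint at 240 treated subjects, and states: "The IDMC will be provided with blinded efficacy data at the time of the interim analysis". The next sentence is "Detail of the activities associated with the IDMC will be provided in an IDMC Charter". The following paragraph says that, in deciding whether to recommend early termination, "the IDMC shall be guided by a formal stopping rule based on the primary efficacy endpoint", and defines the statistic: "The test statistic shall be the estimated difference in the probability of TTH within 6 minutes between the HEMOBLAST™ and G+T arms". The look is expected to include "approximately 160 subjects treated with HEMOBLAST™ under 2:1 randomization", which leaves about 80 on G+T. Table 9 gives the interim cut-offs as Z 0.788 for futility and 2.373 for efficacy. SAP 10.7.1 and its Table 3 repeat all of this.

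Three other places bear on the point:

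- Protocol 8 sets up the committee "to review data from the clinical investigation to evaluate the safety and efficacy of the investigational device". It adds "A separate charter for the IDMC will define and describe", among other things, roles and responsibilities, and documentation and reporting.
- Protocol 12.4.3 and SAP 10.7.2 name an independent statistical group that prepares the IDMC's reports and recalculates the maximal sample size. That recalculation is called blinded and uses the success rate pooled over arms.
- SAP 8.3 blinds the subjects and mentions nobody else.

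**The concern.** The stopping statistic is a difference between arms, so nobody can apply the rule from data that hide the arms. If blinded meant pooled for the IDMC, as it does for the sample-size recalculation, the committee could not tell whether a boundary had been crossed. Coded arms would conceal little, because a 160:80 split shows which group is HEMOBLAST.

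The stake is traceability. This look can end a pivotal trial with a non-inferiority conclusion while enrollment continues and investigators score hemostasis themselves. A reader would want to see who held the codes, who computed Z and what the committee saw. The documents give the reporting group two tasks, preparing IDMC reports and recalculating sample size, and do not expressly add the interim Z.

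**Working it through.** **1. The plan's own figures.** Inputs from Protocol 12.4.1, Table 9 and 12.4.2: success 0.88 in both arms, margin 0.10, 160:80 at the interim and 267:133 at the end, cut-offs 0.788 / 2.373 / 2.036, information fraction 240/400 = 0.60.

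SE = √[p(1−p)(1/nH + 1/nG)]

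- Interim: √[0.88 × 0.12 × (1/160 + 1/80)] = 0.0445, so the expected Z is 0.10/0.0445 = 2.25.
- Final: √[0.88 × 0.12 × (1/267 + 1/133)] = 0.0345, so the expected Z is 0.10/0.0345 = 2.90.

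Treating the two Z-statistics as bivariate normal with correlation √0.60:

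- Power = P(Z1 ≥ 2.373) + P(0.788 < Z1 < 2.373, Z2 ≥ 2.036) = 0.4500 + 0.3503 = 0.8003. The plan states about 80.1%.
- One-sided alpha, with futility ignored because it is non-binding = 0.0088 + 0.0162 = 0.0250, as stated.

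Neither figure depends on who calculates Z or in what form it reaches the committee.

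**2. Could pooled data drive the rule?** Hold the pooled result at 211/240 (87.9%, close to the design rate) and vary the split. The formula is Z = (pH − pG + 0.10)/√[pH(1−pH)/160 + pG(1−pG)/80]. It is unstratified; the stratified Cochran-Mantel-Haenszel version could move a cut-off slightly.

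| HEMOBLAST /160 | G+T /80 | Difference | Z | Rule says |
|---|---|---|---|---|
| 142 | 69 | +0.025 | 2.72 | stop, efficacy |
| 141 | 70 | +0.006 | 2.36 | continue |
| 138 | 73 | −0.050 | 1.20 | continue |
| 137 | 74 | −0.069 | 0.77 | stop, futility |

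Pooled counts therefore cannot operate the rule. This is true of any between-arm test: with this formula all three outcomes are possible at every pooled total from 7 to 226 of 240. The table rules out one reading of the sentence. It does not measure a risk in this trial.

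**3. The possible readings.**

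- *Pooled over arms.* The rule fails. But the plan uses that meaning only for the sample-size recalculation, and applying it to the IDMC report would contradict the paragraph that follows.
- *Coded arms.* The rule works. The 160:80 split identifies the arms, and the committee needs to know the direction: 137/160 against 74/80 gives Z = 0.77 with the labels right and (0.069 + 0.10)/0.0405 = 4.17 with them exchanged.
- *Z or boundary status supplied by the reporting group.* The rule works, and the committee need not see subject-level codes.

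Two of the three readings let the rule run. The one that does not is the one the plan's own stopping rule excludes.

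**The case for a change.** The strongest case for acting is that the only sentence describing the efficacy data the IDMC receives calls them blinded, and it stands in both documents. A Charter that gave the committee comparative results would sit awkwardly beside it. Protocol 12.4.3 passes further detail on implementing the boundary to the SAP, and SAP 10.7.2 still does not say who computes Z. Rewording would cost a sentence in each document.

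The description of the text is right: the word is undefined for the IDMC, and the task is not expressly assigned. But this does not make the rule inoperable. The reporting group is named under the heading on implementing the stopping boundary, and it already prepares the committee's reports. Sending roles and reporting to a Charter is an ordinary division of labor, and the plan announces it directly after the disputed sentence. Whether the Charter covers the point cannot be judged from the documents reviewed. A rule keeping the sponsor and investigators blinded to aggregate interim results might be good practice, but it is a separate matter that this wording does not decide.

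**Conclusion.** No change to the plan follows. The wording is loose, and the gap is one that the reporting group and the IDMC would fill sensibly. The only workable course is for someone with the codes to supply Z or boundary status, and the independent reporting group is the natural source. The statistic, its standard error, the sample size at the look, both cut-offs (the efficacy one introduced by "Alternatively, if the observed Z-statistic for testing non-inferiority is 2.373") and the decision attached to each are fixed in advance. A recommendation can therefore be checked against the rule afterwards. The IDMC is guided by the rule, and futility is non-binding.

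The effect on the results is nil: alpha stays at 0.0250, power at about 80%, the maximal sample size at 400 before any recalculation, and the boundaries are unchanged. This rests on two assumptions: that the reporting group has access to the treatment codes, and that the Charter does not restrict the IDMC to pooled data. Neither can be confirmed from the protocol and SAP, and nothing in them contradicts either.

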12.4.2 Sample Size Justification

The sample size for the proposed study is based on a level 0.025 (one-sided) test to exclude a probability of TTH within 6 minutes that is 10% less among subjects treated with HEMOBLAST™ compared to those treated with G+T. The maximum number of subjects enrolled will be computed as to provide approximately 80.1% power to declare comparable efficacy when the two treatments have the same probability of TTH within 6 minutes. The variance estimate in the sample size calculation assumes an 88% 6 minute hemostasis success rate in both the HEMOBLAST™ and G+T arms. The planned stopping rule will implement a single interim analysis after outcome data have been observed on 240 treated subjects. If the study were to continue to the final analysis with a decision in favor of comparable efficacy, it is anticipated that efficacy data would be available on 400 treated (approximately 267 patients treated with HEMOBLAST™ under a 2:1 randomization scheme). Assuming equal accrual to each surgical indication this would provide efficacy data on roughly 89 subjects treated with HEMOBLAST™ for each surgery type.

The variance of a proportion is dependent on the proportion itself. Hence, power for the study will be partially determined by the probability of TTH within 6 minutes on each of the treatment arms. Under the design assumption that the probability of TTH within 6 minutes on the G+T arm is 88%, the study will require a maximum of 400 treated subjects to attain approximately 80.1% power to declare comparable efficacy based upon a 10% non-inferiority margin. As discussed in Section 12.4.3, in order to maintain approximately 80.1% power should a larger variance be observed, a flexible sample size based on statistical information from pooled trial data will be used.²³

12.4.3 Implementation of the Stopping Boundary

Modifications of the stopping rule to account for changes in the schedule of the interim analysis and estimates of variability will be made by using the parametric form of the stopping rule as specified above, a blinded sample size recalculation will be performed prior to the interim analysis. An independent statistical reporting group preparing reports for the IDMC will use the constrained boundaries method as implemented in S+SeqTrial® to recalculate the maximal sample size based on the marginal response rate observed in the study at the time of the pre-planned interim analysis (marginalized over treatment arms).²³ The one-sided type I error rate for the study will be maintained at 0.025, and the maximal sample size will

be adjusted up to maintain 80.1% power provided that the recalculated maximal sample size is 460 treated subjects or less within the TTH Population as defined in 12.3.1.1. Further details of the implementation of the stopping boundary will be provided in the Statistical Analysis Plan.

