1 SYNOPSIS

Title	Prospective, Randomized, Controlled, Multicenter, Pivotal, Clinical Investigation Evaluating the Safety and Efficacy of HEMOBLAST™ Bellows in Cardiothoracic, Abdominal, and Orthopedic Lower Extremity Surgeries
Investigational Plan Number	ETC 2015-002
Purpose/Objectives	To evaluate the safety and efficacy of a new hemostatic device (HEMOBLAST™ Bellows) compared to a control device, absorbable gelatin sponge USP with thrombin.
Indication	HEMOBLAST™ Bellows is intended for use in surgical procedures as an adjunct to hemostasis when control of bleeding by conventional procedures is ineffective or impractical, except in neurosurgical, ophthalmic, and urological procedures.
Study Design	Prospective, randomized, controlled
Number of Subjects/Sites	A maximum of 450 subjects enrolled across a maximum of 25 investigational sites. A maximum of 50 lead-in subjects will be enrolled, with 400 subjects randomized, enrolled, and included in the primary analysis for efficacy; all subjects will be evaluated for safety.
Preoperative Inclusion Criteria	
A subject must meet all of the following preoperative inclusion criteria to be enrolled into the investigation:
 
 • Subject is undergoing an elective open cardiothoracic, abdominal, or orthopedic lower extremity surgery; • Subject or an authorized legal representative is willing and able to give prior written informed consent for investigation participation; • Subject undergoing cardiothoracic surgery is not allergic to protamine; and • Subject is 21 years of age or older.

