2.4.2 Number of Subjects and Investigational Sites

A maximum of 450 subjects will be enrolled across a maximum of 25 investigational sites in the United States. Four hundred patients will be randomized, enrolled, and evaluated for efficacy (Time to Hemostasis [TTH] Population). There will be a maximum of 50 lead-in subjects (one per enrolling investigator).

On average, approximately 18 subjects will be enrolled per site, with no more than 15% of the total TTH Population (60 subjects) being enrolled at any single site.

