5.5 Subject Selection Criteria

A maximum of 450 (400 efficacy, maximum of 50 lead-in) subjects undergoing elective open cardiothoracic, abdominal, and orthopedic lower extremity surgeries will be enrolled into the clinical investigation. Subjects will need to meet all eligibility criteria to be enrolled into the investigation, as detailed below.

5.5.1.1 *Preoperative Inclusion Criteria*

A subject must meet all of the following preoperative inclusion criteria to be enrolled into the investigation:

- Subject is undergoing an elective open cardiothoracic, abdominal, or orthopedic lower extremity surgery;
- Subject or an authorized legal representative is willing and able to give prior written informed consents for investigation participation;
- Subject undergoing cardiothoracic surgery is not allergic to protamine; and
- Subject is 21 years of age or older.

5.5.1.2 *Preoperative Exclusion Criteria*

A subject must not meet any of the following preoperative exclusion criteria to be enrolled into the investigation:

- Subject is undergoing a laparoscopic, thoracoscopic or robotic surgical procedure;
- Subject is undergoing a neurologic surgical procedure;
- Subject is undergoing a spinal surgical procedure;
- Subject is undergoing an emergency surgical procedure;
- Subject is pregnant, planning on becoming pregnant during the follow-up period, or actively breast-feeding;
- Subject has a clinically significant coagulation disorder or disease, defined as a platelet count < 100,000 per microliter or International Normalized Ratio > 1.5 within 4 weeks of surgery;
- Subject receiving intravenous heparin within 12 hours before surgery or oral Coumadin within 2 days before surgery;
- Subject receiving antiplatelet medications within 5 days prior to surgery;
- Subject undergoing abdominal or orthopedic lower extremity surgery receiving aspirin within 7 days prior to surgery;
- Subject has an active or suspected infection at the surgical site;
- Subject has had or has planned to receive any organ transplantation;
- Subject has a known sensitivity or allergy to bovine and/or porcine substance(s) or any other component(s) of the hemostatic agent;
- Subject has ASA classification of 5³;
- Subject has a life expectancy of less than 3 months;
- Subject has a known psychiatric disorder, which in the opinion of the Principal Investigator, would preclude the subject from completing this clinical study;

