6.4.2 Randomization and Hemostat Application

At the start of each surgical procedure, a single HEMOBLAST™ device and a single G+T device will both be prepared per the respective Instructions for Use (unless the subject is a lead-in subject; all lead-in subjects will have a single HEMOBLAST™ device prepared). The preparation time for both devices will be recorded for the TTH Population subjects.

Randomization will be performed through sequentially numbered sealed envelopes. Four-hundred subjects (TTH Population) will be randomized to receive HEMOBLAST™ or G+T in a 2:1 ratio:

- 267 subjects will be randomized to receive HEMOBLAST™; and
- 133 subjects will be randomized to receive G+T.

There will be a maximum of 50 lead-in subjects; these subjects will not be randomized. The first subject for each investigator will be treated as a lead-in subject. These subjects will receive HEMOBLAST™ and will be followed for safety only (maximum Full Analysis Population of 450); lead-in subjects will not count towards the TTH Population. Please see Section 12 below for additional detail on subject populations.

Randomization will be stratified by surgical indication and will incorporate blocking; additional details of randomization and blocking will be included in a separate Randomization Plan.

After randomization and enrollment, the assigned hemostat will be used in the investigational subject; the other hemostat will be discarded following institutional procedures.

A study-specific stopwatch will be used to track hemostat application and the times of hemostasis evaluation. The time of initial hemostat application will be considered time 0; at this time, the stopwatch will be started by the study coordinator. The stopwatch will run continuously without stopping.

Hemostasis will be evaluated by the investigator at the following time points until hemostasis has been achieved:

- 3 minutes;
- 6 minutes; and
- 10 minutes.

Reapplication of the randomized hemostat will be performed at the 3 minute and 6 minute evaluation time points, as described below.

For cardiothoracic procedures, the TBS will be identified after heparin reversal. Additionally, the TBS will not be at the site of a valve implant or at the site of a synthetic graft or patch implant.

HEMOBLAST™ will be applied according to its instructions for use.

1. Peel open the pouches to remove contents with attention to sterile procedures.
2. Remove cap using a twisting motion.

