12.3 Analytic Methods

12.3.1 Analysis of Primary and Secondary Efficacy Endpoints

12.3.1.1 Analysis Population

Efficacy analyses will be conducted on the TTH Population, defined as all subjects who were randomized, received study intervention, and had a TTH assessment recorded regardless of whether the measurement was censored. Lead-in subjects are *not* part of the TTH Population.

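### Re-estimation may raise the efficacy population to 460 treated subjects, lead-ins excluded, while the same documents limit the whole trial, lead-ins included, to 450

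*Protocol*

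**What the plan says.** **The re-estimation ceiling.** Protocol 12.4.3 provides for a blinded recalculation of the maximal sample size, based on the success rate pooled over arms, before the interim analysis at 240 subjects. The maximal size will "be adjusted up to maintain 80.1% power provided that the recalculated maximal sample size is 460 treated subjects or less", counted within the TTH Population. SAP 10.7.2 repeats the rule with the same figure.

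**Who counts towards it.** The definition that Protocol 12.4.3 refers to, in 12.3.1.1, states: "Lead-in subjects are *not* part of the TTH Population". SAP 10.5.1 says the same. Protocol 12.4.1 counts up to 50 lead-ins in addition to the TTH Population when it describes the safety data.

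**The enrolment limit.**
- Protocol synopsis: "A maximum of 450 subjects enrolled across a maximum of 25 investigational sites".
- Protocol 2.4.2: "A maximum of 450 subjects will be enrolled across a maximum of 25 investigational sites in the United States", followed by a site limit of "no more than 15% of the total TTH Population (60 subjects) being enrolled at any single site".
- Protocol 5.5: "A maximum of 450 (400 efficacy, maximum of 50 lead-in) subjects undergoing elective open cardiothoracic".
- Protocol 6.4.2: "maximum Full Analysis Population of 450", with 267 and 133 randomized. It also says "The first subject for each investigator will be treated as a lead-in subject".
- SAP 8.2 repeats the Full Analysis Population maximum of 450. SAP 8.1 gives 450 as a total, of which fifty are roll-in subjects.

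None of these sections mentions re-estimation.

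**The concern.** Protocol 12.4.2 and SAP 8.4 name the flexible sample size as the way to keep about 80.1% power if the variance is larger than planned. It works only if the trial may enrol the extra subjects. Two limits apply to the same enrolment: one allows 460 efficacy subjects with lead-ins on top, and the other stops the trial at 450 with lead-ins included. If the recalculation asked for more subjects, someone would have to decide during the trial which limit governs. The result would be either an avoidable amendment while enrolment is running (Protocol 12.4.1 has enrolment continue in parallel with the interim analysis) or a loss of the power that the re-estimation was meant to protect.

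**Working it through.** **1. The plan's own figure.** Inputs, from Protocol 12.4.1, 12.4.2 and Table 9: success rate 88% in both arms, margin 0.10, one-sided 0.025, allocation 2:1, maximal size N = 400, interim at 240 (information 240/400 = 0.6), futility Z 0.788, efficacy Z 2.373, final Z 2.036.

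- Variance of the difference = p(1 − p) × [1/(2N/3) + 1/(N/3)] = p(1 − p) × 4.5/N.
- At p = 0.88: 0.1056 × 4.5/400 = 0.001188, so SE = 0.03447.
- Expected Z at the final analysis = 0.10/0.03447 = 2.90. At the interim it is 2.90 × √0.6 = 2.25.
- Power = P(Z1 ≥ 2.373) + P(0.788 < Z1 < 2.373 and Z2 ≥ 2.036), with correlation √0.6. Bivariate normal integration gives 80.07%, against 80.1% stated. The one-sided type I error with the futility boundary ignored is 0.0250.

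The design is reproduced, with futility stops followed.

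**2. The two limits.**

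| Lead-ins enrolled | Total if the TTH Population reaches 460 | TTH places left under 450 |
|---|---|---|
| 0 | 460 | 450 |
| 25 (assumption: one enrolling investigator at each of 25 sites) | 485 | 425 |
| 50 (the stated maximum) | 510 | 400 |

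The ceiling is 460 − 450 = 10 over the limit before any lead-in is counted, and 510 − 450 = 60 over with 50 lead-ins. In the last row the room left equals the planned 400, so no increase is possible.

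**3. Power if the size is held at 400.** The method of step 1 is used with the same boundaries. They remain appropriate because 240/400 is still 0.6.

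| True rate, both arms | p(1 − p) | SE | Expected final Z | Power |
|---|---|---|---|---|
| 88% | 0.1056 | 0.03447 | 2.90 | 80.07% |
| 87% | 0.1131 | 0.03567 | 2.80 | 77.3% |
| 86% | 0.1204 | 0.03680 | 2.72 | 74.7% |

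The loss against 80.07% is 2.8 points at 87% and 5.4 points at 86%. These are normal approximations. A simulation with binomial counts gives 82.0% at 88% and N = 400, about 2 points higher, so the size of the fall is more reliable than the levels.

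**The case against.** The strongest reply is that 450 is the base-case total. It is 400 + 50 (Protocol 5.5), Protocol 12.4.2 makes 400 the maximum under the 88% assumption and then allows a flexible size, and SAP 8.1 speaks of a total and not of a maximum. This is a plausible account of what was intended. It does not remove the conflict, because the synopsis, Protocol 2.4.2, 5.5 and 6.4.2 and SAP 8.2 all call 450 a maximum, and no section says that it may rise. The site limit is less of a problem: 15% scales with the TTH size, and only the 60 in parentheses is tied to 400.

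Four stronger readings might be inferred, and the documents do not support them.

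- *Type I error is at risk.* The recalculation uses only the pooled rate, and both documents re-adjust the boundaries to hold 0.025.
- *The re-estimation can never work.* That is so only at 50 lead-ins. With fewer, part of the increase fits.
- *The conflict arises only through the lead-ins, or at particular pooled counts at the interim.* The 460 ceiling alone exceeds 450. Which counts call for which size depends on the constrained boundaries method, with the interim at 240/N of the information. Scaling 400 by the variance holds the interim at 60% and gives somewhat different sizes, so no trigger counts or breach frequencies are offered here.
- *The rule is undefined above 460.* The wording is a condition: above 460 there is no increase. Preferring an increase up to 460 in that case is a design choice, not a correction.

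**Conclusion.** The inconsistency is real and follows by addition: up to 510 subjects are permitted by one rule and 450 by the other. Depending on the number of lead-ins, the enrolment limit blocks part or all of the re-estimation. If all of it is blocked, power is about 77% at 87% and about 75% at 86%. Those power figures assume equal true rates in the two arms, an interim at 240 of 400, the Table 9 boundaries with futility followed, and no stratification. How often the limit would be reached is not quantified. The validity of the test is not in question; what is at stake is power or a mid-trial amendment. It should be corrected, and correction is cheap.

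**What to change.** State one consistent maximum in both documents, in one of two ways.

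1. **Allow the increase.** In the synopsis, Protocol 2.4.2, 5.5 and 6.4.2 and SAP 8.1 and 8.2, say that 450 is the total before re-estimation and that the maximum after it is 460 TTH subjects plus up to 50 lead-ins, 510 in all. Update the figures tied to 400: the 267/133 split (about 307/153 at 460), and the 60-subject site figure, restated as 15% of the final TTH size (0.15 × 460 = 69). The average of about 18 per site (450/25) would become 510/25 = 20.4.
2. **Keep 450.** In Protocol 12.4.3 and SAP 10.7.2, replace 460 by 450 minus the lead-ins enrolled, and say that 80.1% power is then maintained only as far as that ceiling allows.

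Optionally, add one sentence to Protocol 12.4.3 and SAP 10.7.2 confirming that a recalculated size above the ceiling means no increase.

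The cost is wording only. The first option raises the stated maximum enrolment by 60. The second gives up some or all of the re-estimation.
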